Data were collected on-line via a free and open iOS application, “DiagnosUs”, created by Centaur Labs as a platform for game-like image labeling competitions <https://www.centaurlabs.com/>). Between 6/22/21 and 6/27/21, Centaur Labs ran 24 ‘contests’ on our behalf, collecting >300,000 trials from 803 participants in 6 days. Each of the 24 contests consisted of 80 unique images of a skin lesion as shown in Figure 1. This is a relatively small number of images, but it kept the sessions short and encouraged participation. Images came from the International Skin Imaging Collaboration (ISIC) 2018 challenge (Codella, et al., 2019). The set contains over 1,200 melanoma images and over 7,600 nevus images.

[figure not shown]

Figure 1: Sample stimulus displays. Left: Participants are asked if a lesion is a melanoma (cancer) or a nevus (benign ‘mole’). Right: After response, if this were a feedback condition, red or green feedback would inform the observer of the correctness of the answer. In no feedback conditions, neutral feedback indicated that the response had been registered.

On each of the six days, there were four contests available. These were:

- 1) Low Prevalence – No Feedback; consisting of 20% (16) melanoma images
- 2) Low Prevalence – Feedback; prevalence was the same as in #1, but with accurate, trial by trial feedback
- 3) High Prevalence – No Feedback; consisting of 50% (40) melanoma images
- 4) High Prevalence – Feedback; prevalence was the same as in #3, but with accurate, trial by trial feedback

The contests were randomly assigned to participants with the constraint that they did not run the same type of contest more than once in a day. Participants could take part in as many or as few contests as they wished over the course of the six days and they could end up repeating a

condition from one day on another day. The prevalence and feedback conditions were not advertised to participants. Accuracy is the main dependent variable though we also collected response times.

Because of the on-line, voluntary nature of the data collection, we did not have control over the viewing conditions or the type of screen used. We compensated by collecting a very large dataset (see below).

Observers

We collected data from 803 unique individuals. For each individual, we have a crude categorization of expertise as shown in Table 1:

Medical Student	337
Pre-Med Student	174
No Medical Experience	145
Medical Doctor	54
Other Healthcare Professional	47
Nurse	25

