To analyze the effect of one block on the next block, we derived all the pairs of blocks in the dataset. For each of the blocks, we calculated the true positive and false positive proportions and used these to derive the standard signal detection measure of d' and criterion (Note that we are refraining from using the term “sensitivity” because it is used to refer to d' in the behavioral science community and to the true positive rate in the medical community.) For the primary analyses, pairs were removed from analysis if either member of the pair produced a d' of less than 0.5. The task was relatively difficult and we had little control over the motivation of participants in online study of this sort. The probability of achieving a $d' > 0.5$ by guessing through an 80 trial block is $\sim 0.6\%$. A cutoff of 0.4 would permit over 2% of blocks to be pure guessing. A $d' > 0.5$ cutoff left 2,080 pairs of blocks. The distribution of those pairs is shown in

Table 5:

		Block N				
		Low, No Feedback	Low, Feedback	High, No Feedback	High, Feedback	
Block N+1	Low, No	29	140	151	134	454
	Low, Feed	92	110	150	218	570
	High, No	261	117	51	117	546
	High, Feed	147	218	118	27	510
		529	585	470	496	2080

Table 5: Counts of the 16 different pairs of Block N and Block N+1.

As can be seen, there is a good, if uneven distribution of pairs. There are fewer pairs on the diagonal where the condition is the same in Blocks N and N+1. In order to run the same block, twice in a row, participants needed to encounter that condition last on Day K and first on Day K+1 since the same condition could not be run twice on the same day. The marginals show that this distribution of the four different conditions is very roughly uniform.

First, we compare performance in the four conditions, regardless of their position the sequence of sessions for each observer. Figure 2 shows the signal detection measures of d' and criterion, “c”. These values cannot be computed if $p(\text{True Positive}) = 1.0$ or $p(\text{False Positive}) = 0.0$. Accordingly, in keeping with one standard practice, we add $\frac{1}{2}$ of a False Positive error to each False Positive count (Hautus, Macmillan, & Creelman, 2021).

[figure not shown]

Figure 2: D' and Criterion as a function of condition. Each dot represents one of 2080 blocks of data. Black lines show mean and +/- 95% CI of the mean.

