A one-way ANOVA shows a main effect of condition on d' ($F(3, 2076) = 6.461, p = 0.0002$, partial eta-sq = 0.01) and Šídák's multiple comparisons test shows that performance on skin cancer detection task is modestly better in the high prevalence, feedback condition than in the high prevalence, no-feedback condition ($p = 0.008$). Prevalence effects are better understood as criterion shifts. An ANOVA shows a very large main effect of condition on criterion ($F(3, 2076) = 30.16, p < 0.0001$, partial eta-sq = 0.04). Pairwise comparisons show a strong LPE effect when feedback is given ($p < 0.0001$). Criterion becomes more conservative at low prevalence. Without

feedback, criterion becomes slightly more liberal on average (0.34 to 0.31). This is not statistically significant ($p = 0.47$). As noted earlier, the PICC effect (Levari, et al., 2018), while certainly real, is typically more fragile than the LPE effect in the opposite direction (Lyu, et al., 2021). The differences between conditions with feedback and without feedback are highly significant ($p < 0.0001$ for each comparison). A significant LPE effect is seen if analysis is restricted to each participant's first block of data ($p < 0.0001$). There is no PICC effect. If all blocks of data are used, eliminating the $d' > 0.5$ filter, there is, again a significant LPE ($p < 0.0001$) and an insignificant PICC effect ($p = 0.1244$).

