Looking separately at changes in P(True Positive) and P(False Positive) responses, we see essentially the same pattern of results. For changes in True Positive proportions, pairs where Block 1 is low prevalence with feedback are significant (all $p < 0.005$) except when Block 2 is High Feedback ($p = 0.38$). Pairs where Block 1 is high prevalence with feedback are significant (all $p < 0.005$ except when Block 2 is Low Feedback which $p = 0.02$). The Low Feedback – High Feedback pair is not significant. For changes in False Positive proportions, pairs where Block 1 is low prevalence with feedback are significant (all $p < 0.05$). When Block 1 is high prevalence with feedback, results are significant when Block 2 is Low No Feedback, High No Feedback, and Low Feedback ($p < 0.01$). When Block 2 is High Feedback, there is no significant change ($p = 0.29$). The Low No Feedback – High Feedback pair is significant ($p = 0.001$). No other changes in P(True Positive) and P(False Positive) responses are significant. As noted above, removing the $d' > 0.5$ filter does not change the pattern of results. Limiting analysis to only the first pair of blocks for each participant preserves the direction of effects but some effects become statistically unreliable because of the loss of power.

Do the effects of one block on the next change with time between blocks?

Figure 5 shows that a block with feedback has an influence on the criterion in the next block. Is that effect transitory or persistent? The time between blocks is quite variable because participants could perform the second block immediately or from one to several days later. Accordingly, for each of the 16 pairs of blocks, we examined change in criterion as a function of time between blocks. The results are shown for four different time ranges in Figure 6.

[figure not shown]

Figure 6: Change in criterion as a function of time between the start of block 1 and start of block 2. 1440 minutes = 1 day. Colored lines are best-fit linear regressions for each of 16 pairs of block types. A) All data, B) Delay < 1 day, C) Delay < 2 hours, D) Delay < 15 min. Repeat pairs (e.g. Low Feedback -> Low Feedback) do not occur for shorter delays (C & D).

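### The stated 0.6% chance of passing the d' > 0.5 filter by guessing is too low: the block sizes give about 3-5% at high and 7-8% at low prevalence (guesser answering 'melanoma' half the time)

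*Combined protocol and SAP*

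**What the plan says.** Under Statistical Analysis / Results, the specific protocol computes d' and criterion for each block from the true and false positive proportions. For the primary analyses, "pairs were removed from analysis if either member of the pair produced a d' of less than 0.5". This leaves 2,080 pairs.

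Two figures support the choice of 0.5. The first is "The probability of achieving a $d' > 0.5$ by guessing through an 80 trial block is $\sim 0.6" per cent. The second is offered against a looser rule: "A cutoff of 0.4 would permit over 2% of blocks to be pure guessing". The calculation is not shown, no guessing rate is given, and the two prevalence levels are not separated.

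Block composition is fixed in the Methods: 80 images per contest, with "Low Prevalence – No Feedback; consisting of 20% (16) melanoma images" and "High Prevalence – No Feedback; consisting of 50% (40) melanoma images". The feedback versions have the same prevalences. To handle extreme proportions, half a false positive is added to each false positive count. The text does not say whether the denominator changes, or how a true positive proportion of 1 is treated.

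The filter was also lifted as a check. On the comparison of conditions: "If all blocks of data are used, eliminating the $d' > 0.5$ filter, there is, again a significant LPE". On the block-to-block effects: "removing the $d' > 0.5$ filter does not change the pattern of results".

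**The concern.** A d' from a single block is imprecise, because its sampling error depends on the separate numbers of target and non-target images, not on the total of 80. With 40 of each, or only 16 melanomas, chance alone should push a guesser above 0.5 far more often than 6 times in 1,000. A single figure for both prevalence levels is also suspect, because the 16/64 split gives a noisier d' than the 40/40 split.

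The two percentages are the only numerical reason given for the rule that defines the primary analysis set. If they are wrong, readers will think the retained blocks are better screened against guessing than they are. They will also not see that the screen works differently across prevalence, which is one of the two factors the study manipulates.

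**Working it through.** **Inputs.** From the Methods: 80 images per block; low prevalence 16 melanoma and 80 - 16 = 64 nevus; high prevalence 40 and 40. From Statistical Analysis / Results: d' from true and false positive proportions, cutoff 0.5, alternative 0.4. Assumed: a guesser answers 'melanoma' with the same probability g on every image; base case g = 0.5, then varied.

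**Formula.** Hits ~ Binomial(n_mel, g) and false alarms ~ Binomial(n_nev, g), independent. d' = z(hits / n_mel) - z(false alarms / n_nev). The pass rate is the total probability of all outcomes with d' above the cutoff. As the edge correction is only partly specified, four were run: (a) proportions clipped at 1/(2n); (b) log-linear on both; (c) +0.5 on the false positive count over n_nev, true positives clipped; (d) the same over n_nev + 1.

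**Trying to reproduce the stated figures.** With the actual block sizes, no g from 0.1 to 0.8 under any of the four corrections gives 0.6%. Two calculations that do not fit the design come close to both stated figures:

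- 80 targets plus 80 non-targets: 0.58% at 0.5 and 2.2% at 0.4 (normal approximation).
- The two-alternative forced-choice formula on 80 trials: 0.67% and 2.3%.

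Where the stated figures actually came from is unknown.

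**Exact results, g = 0.5, single block.**

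| Cutoff | Block | (a) | (b) | (c) | (d) | Stated |
|---|---|---|---|---|---|---|
| 0.5 | 40/40 | 4.65% | 3.29% | 2.88% | 4.35% | ~0.6% |
| 0.5 | 16/64 | 8.37% | 6.99% | 7.50% | 8.37% | ~0.6% |
| 0.4 | 40/40 | 7.33% | 7.29% | 7.28% | 7.36% | over 2% |
| 0.4 | 16/64 | 12.91% | 12.15% | 12.24% | 12.89% | over 2% |

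**Check by normal approximation.** At g = 0.5, SE(d') = sqrt[0.25 / 0.3989² × (1/n_mel + 1/n_nev)].

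- 40/40: SE = 0.280; 0.5/0.280 = 1.78, upper tail 3.7%. At 0.4: 7.7%.
- 16/64: SE = 0.350; 0.5/0.350 = 1.43, upper tail 7.7%. At 0.4: 12.7%.

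A pass rate of 0.6% would correspond to d' of about 0.70 (40/40) or 0.88 (16/64).

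**Sensitivity to g, cutoff 0.5, range over the four corrections.**

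| g | 40/40 | 16/64 |
|---|---|---|
| 0.1 | 6.2-11.7% | 9.4-13.8% |
| 0.2 | 4.7-7.0% | 7.6-9.6% |
| 0.37-0.38 | 3.1-4.6% | 6.9-8.0% |
| 0.5 | 2.9-4.7% | 7.0-8.4% |
| 0.8 | 5.4-7.1% | 9.6-15.1% |

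The third row uses the mean criterion reported without feedback ("criterion becomes slightly more liberal on average (0.34 to 0.31"): Phi(-0.34) = 0.367 and Phi(-0.31) = 0.378. Over g from 0.1 to 0.7 the minimum is 2.86% (40/40) and 6.85% (16/64).

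**Pairs.** If both blocks are guessed, the pass rates multiply. At g = 0.5 and cutoff 0.5:

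- high-high: 0.0288² to 0.0465² = 0.08-0.22%
- mixed: 0.22-0.39%
- low-low: 0.0699² to 0.0837² = 0.49-0.70%

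The low-low figure brackets 0.6%, but the sentence refers to one 80-trial block. The same squaring at 0.4 gives 0.1215² to 0.1291² = 1.5-1.7%, which is not over 2%. If only one block of the pair is guessed and the other genuinely passes, the pair survives at the single-block rate.

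**Prevalence contrast.** At g = 0.5 the low/high ratio of pass rates runs from 8.37/4.65 = 1.8 to 7.50/2.88 = 2.6.

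**The case against.** The strongest reply is that nothing of substance depends on the figure. The document reports the same pattern without the filter, both blocks of a pair must pass, and these are pass rates given guessing, not the share of guesses among the 2,080 pairs, which is unknown. All of that stands, and it limits the consequence. It does not make the stated probability correct.

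Second, the choice of 0.5 over 0.4 keeps its direction: the stricter cutoff does admit fewer guessed blocks (at g = 0.5, about 7.3% falls to 2.9-4.7% at high prevalence, and 12-13% to 7-8% at low). The text never formally makes 2% a limit, and 'over 2%' is literally true of 7% or 13%. That is fair. But the argument against 0.4 is that it lets through more than 2%, and 0.5 does so too at both prevalences.

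Third, the recomputed figures depend on an assumed guessing rate, and the reported mean criterion comes from blocks that had already passed the filter, so it need not describe guessers. This also stands, and the figures should always carry the assumption. It does not rescue 0.6%: more biased guessing mostly raises the pass rate. The low-prevalence rate falls below the range shown only when the guesser calls nearly every lesion melanoma (1.8% at g = 0.95 under one correction).

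Fourth, the low/high ratio is itself assumption-bound (near 1.0-1.5 at g = 0.1), and no effect on the criterion results is shown. Agreed; it is a point for disclosure.

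**Conclusion.** The concern holds. For a guesser answering 'melanoma' half the time, the single-block pass rate at d' > 0.5 is 2.9-4.7% at high prevalence and 7.0-8.4% at low prevalence, against a stated 0.6%. That is about 5-8 times and 12-14 times the stated figure. The conclusion rests on the block sizes in the Methods, the standard yes/no d', and an assumed guessing rate. Varying that rate from 0.1 to 0.7 leaves every value above 2.8% (high) and 6.8% (low).

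The numerical case for 0.5 over 0.4, as worded, does not survive, though 0.5 remains the stricter screen. No bias in a reported result is shown, and the cutoff itself need not change. This should be fixed because it is a wrong number relied on to define the primary set; it does not threaten the main finding.

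**What to change.** Replace the two sentences on guessing with text such as: 'Assuming a guesser answers melanoma on half the trials, a guessed block exceeds d' = 0.5 about 3-5% of the time at high prevalence (40/40) and 7-8% at low prevalence (16/64); for a cutoff of 0.4 the figures are about 7-8% and 12-13%. Because both blocks must pass, a pair guessed in both survives less than 1% of the time under this assumption. The main pattern is unchanged when the filter is removed.'

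State the edge correction in full, including the denominator and the treatment of a true positive proportion of 1; the ranges above can then become single values. Word the figures as the pass rate of a guessed block, not as a share of blocks. Keep one common cutoff, and cite the unfiltered analysis already run as the support for robustness.

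Cost: a text change only, with no new data and no re-analysis.

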each of these effects, we derive measures of d' and criterion for each of the 16 pairs (combinations of one of four 'first blocks' with one of four 'second blocks'). We then subtract a baseline derived from all blocks of the second block condition. We use the second blocks as the baseline because we are looking for a change in the second block. In fact, it doesn't make much difference. Many second blocks in one pair are the first blocks in a subsequent pair and the baselines would be very nearly the same if all blocks were included as in Figure 2 above. Thus, for example, to assess the influence on criterion of Low Prevalence without Feedback (Condition 1 in the figures to follow) on High Prevalence without Feedback (Cond 3), we compute $\text{Criterion}(\text{pair 13}) - \text{Criterion}(\text{Cond 3})$. This is done for each of the 2080 pairs of blocks using the $d' > 0.5$ filter. The data for each of these 2080 "good" pairs of blocks are posted on the Open Science Framework at <https://osf.io/hck5n/>.

Figure 4 shows the change in D' as a function of pair with each dot representing one pair of blocks. Statistical tests are simple T-tests against a null hypothesis of no change in d' from block 1 to block 2. Three pairs, forming no obvious pattern, reach statistical significance (all $p = \sim 0.02$, all Cohen's $d = \sim 0.2$). As these are not corrected for multiple comparisons, these should not be considered strong effects. The general picture is of little or no effect of the first block of trials on d' in the second block of trials.

[figure not shown]

Figure 4: Change in d' on block 2 as a function of the nature of block 1. X-axis gives numerical values for each member of a pair where 1 = low prevalence, no feedback, 2 = low prevalence, with feedback, 3 = high prevalence, no feedback, and 4 = high prevalence, with feedback. P-values show results for simple t-tests, testing against the null hypothesis that there is no change in d' . Black lines show means +/- 95% confidence intervals.

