Because the distribution of delays is strongly skewed toward shorter delays, we repeated the regression analysis separately for the whole dataset, for all delays < 1 day (84% of all data), < 2hrs (60% of all data), and 15 min or less (still include 52% of all data because participants tended to do one block and then another, immediately). The four panels of Figure 6 zoom in to smaller and smaller time scales but, in fact, it does not matter. The point of the admittedly noisy Figure 6 is that there is no obvious pattern of slopes. This is borne out by linear regressions for

each of the 16 pairs of block types. For the entire data set (Figure 6A), fourteen of sixteen correlations are not significant (all $r\text{-sq} < 0.02$, all $p > 0.16$). The Low No Feedback -> Low Feedback Pair has a $r\text{-sq}$ of 0.06 ($p = 0.015$). The High Feedback -> Low Feedback Pair has a $r\text{-sq}$ of 0.02 ($p = 0.045$). The regression lines for those conditions are shown as thicker lines in Fig 6A. Examining this relationship, the change in criterion is near zero at short times and the change grows more conservative with time. For delays less than 1 day, no correlations are significant (all $r\text{-sq} < 0.02$, all $p > 0.35$). For delays less than 2 hrs, no correlations are significant (all $r\text{-sq} < 0.02$, all $p > 0.20$). For delays less than or equal to 15 min, no correlations are significant (all $r\text{-sq} < 0.025$, all $p > 0.24$). In sum, there is no evidence for the effects, shown in Figure 4, fading with time. The two (out of 64) significant correlations seem likely to be random fluctuations of the data and go in the 'wrong' direction if the hypothesis under test is that block 1 would influence block 2 if block 2 occurred recently but not after a longer delay.

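### The four repeat-condition cells occur only across a day change but are measured against a baseline of all second blocks, so they cannot separate carry-over from a start-of-day effect; the main finding does not depend on them.

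*Combined protocol and SAP*

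**What the plan says.** All references are to the Specific Protocol in the combined protocol and SAP.

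- **Assignment.** Methods describes four contests a day for six days, with no contest type repeated within a day. Statistical Analysis / Results gives the consequence when explaining the thin diagonal of Table 5: to repeat a condition, "participants needed to encounter that condition last on Day K and first on Day K+1".
- **Baseline.** Under the heading How does one block influence the next?, a change score is formed for each pair: "We then subtract a baseline derived from all blocks of the second block condition". Only second blocks enter the baseline. No matching on delay, position in the day or study day is mentioned.
- **Main finding.** Criterion is reported to shift conservatively in all four cells that follow low prevalence with feedback (p < 0.006). It shifts liberally in all four that follow high prevalence with feedback (p < 0.0005, but p = 0.017 for pair 44, n = 27). Cohen's d is given as 0.2 to 0.5.
- **Delay.** The section on time between blocks measures delay as the "time between the start of block 1 and start of block 2". It describes two of the subsets as "for all delays < 1 day (84% of all data), < 2hrs (60% of all data". A further cut at 15 minutes keeps 52%, which the authors put down to people moving straight from one block to another. The Figure 6 legend adds: "Repeat pairs (e.g. Low Feedback -> Low Feedback) do not occur for shorter delays (C & D".
- **Figure 7.** Figure 5 is repeated with the 40% of data whose delay exceeds two hours. The text does not say whether the baseline was rebuilt.

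**The concern.** In the diagonal cells, having the same condition as before and opening a new day always coincide. None of their second blocks can fall on the first study day, and none follows its predecessor within two hours. The reference they are compared with is made up mostly of blocks begun soon after the previous one. If people set their criterion differently at the start of a day (warm-up, fatigue late in a run of blocks, a drift over study days), the difference would enter the diagonal cells and be read as carry-over.

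Cells 22 and 44 are cited in support of the main finding. The reported checks do not resolve the matter for them. A delay regression inside a repeat cell has no within-day delays to use. Restricting to delays over two hours keeps every repeat pair, so cells 22 and 44 in Figure 7 rest on the same pairs as in Figure 5. The first-pair-only analysis leaves repeat pairs crossing days as before.

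**Working it through.** **Inputs.** Cell counts from Table 5 (rows are Block N+1, columns are Block N). Delay shares of 84%, 60% and 52% from the section on time between blocks, taken here as shares of the 2,080 pairs. P-values from the text on Figure 5.

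**1. Reproduce the plan's figures.** Second-block totals are 29+140+151+134 = 454, 92+110+150+218 = 570, 261+117+51+117 = 546 and 147+218+118+27 = 510. They sum to 2,080, as stated. For pair 44, inverting a two-sided one-sample t-test (p = 0.017, 26 df) gives t = 2.55 and d = 2.55/√27 = 0.49, inside the stated 0.2 to 0.5.

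**2. Size of the affected set.** Repeat pairs: 29+110+51+27 = 217, or 217/2,080 = 10.4%. Pairs with feedback in block 1: 585+496 = 1,081. Of these, 110+27 = 137 (12.7%) are in cells 22 and 44, and 1,081−137 = 944 are in the other six cells.

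**3. Contrast in delay.** Pairs under two hours: 0.60×2,080 = 1,248. Since no repeat pair is among them, they are 1,248/1,863 = 67% of the non-repeat pairs, against 0% of repeats.

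**4. Bias for a start-of-day shift of delta SD.** If a share f of a condition's second blocks opens a day, the repeat cell, where the share is 100%, is biased by (1−f)×delta. The documents do not give f. Two reference values, assuming short delays are spread evenly over non-repeat pairs:

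| | Cell 22 | Cell 44 |
|---|---|---|
| Repeats as share of own baseline | 110/570 = 19.3% | 27/510 = 5.3% |
| 1−f if every second block after more than two hours opens a day | 0.67×460/570 = 0.54 | 0.67×483/510 = 0.63 |
| 1−f if only the repeats open a day (upper limit) | 0.81 | 0.95 |

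The pooled figure is 0.60. Very roughly 0.5 to 0.6 is a fair working value; it is neither a floor nor a ceiling, because delay by condition is not reported.

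**5. Shift needed to produce a cell's effect alone.** The smallest d that p < 0.006 allows for cell 22 is t/√n = 2.80/√110 = 0.27. The shift needed is 0.267/0.81 = 0.33 to 0.267/0.54 = 0.49 SD. For cell 44 it is 0.491/0.95 = 0.52 to 0.491/0.63 = 0.78 SD.

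**6. Direction.** Cell 22 is conservative and cell 44 is liberal. Their separation is at least 0.27+0.49 = 0.76 SD (equal SDs assumed). With the multipliers 0.54 and 0.63, a common shift alters it by only about 0.09 delta.

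**The case against.** The best defence is that nothing in the documents shows a start-of-day effect, and several results argue against a large one. Fourteen of 16 whole-data delay regressions are non-significant, and none is significant for delays under a day. Cells 11 and 33 share the day-crossing structure and no criterion effect is reported for them. These points stand, with limits. Cells 11 and 33 are small (n = 29 and 51, 95% half-widths about 0.38 and 0.28 SD). The regressions look for a linear trend in minutes, not a step at the day change. The two significant slopes both have low prevalence with feedback as block 2 and move in the conservative direction, as cell 22 does. The authors treat them as chance, which is reasonable: 16×0.05 = 0.8 would be expected, and two or more have probability 0.19 if the 16 tests are independent.

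Three stronger readings are tempting, and the documents do not support them.

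- A reader might infer that a start-of-day effect could account for both feedback clusters, or that the main finding is in doubt. A common shift moves cells 22 and 44 the same way, while their reported effects are opposite. To inflate both, the two feedback conditions would need opposite start-of-day effects, for which there is no evidence. The other six cells are reported at p < 0.006 or p < 0.0005 without any repeat pair among them.
- A reader might assign the bias a definite percentage of the reported effects. That needs a value for delta, and the documents give none.
- A reader might infer that Figure 7 is biased throughout, because repeats are 217/832 = 26% of pairs over two hours and 0% of those under. Figure 7 is read cell by cell, so a pooled share does not bias the test of a non-repeat cell. If its baseline was restricted to the same pairs, it already comes close to the comparison wanted.

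**Conclusion.** The confounding is real and structural, and it is confined to four cells holding 217 of 2,080 pairs. Two of these, 22 and 44, are among the eight cells cited for the main finding. Within them, carry-over and any start-of-day effect cannot be separated as analysed, and neither the delay regressions nor Figure 7 as described does so.

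The likely consequence is modest. The bias is very roughly 0.5 to 0.6 times an unknown shift, and it would enlarge one of cells 22 and 44 while shrinking the other. The main finding is carried by the remaining six cells (944 of 1,081 pairs).

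This rests on the delay percentages applying to the 2,080 analysed pairs, on short delays being spread roughly evenly over conditions, and on equal SDs. If incomplete blocks were dropped before pairing, a repeat's second block might be the first complete block of its day and not the first one begun.

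**What to change.** 1. Add a first-block-of-day indicator and study day (1 to 6) to the carry-over analysis. Alternatively, compare each repeat cell only with other day-crossing second blocks of the same condition.
2. Report cells 22 and 44 both ways. State the main finding on the six non-repeat feedback cells, with 22 and 44 as supportive.
3. For Figure 7, say that the repeat cells reuse the same pairs as Figure 5, and rebuild the baseline from pairs over two hours apart.

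The covariates come from block start times, which the delay analysis already uses. The cost is precision in the four repeat cells, because the reference shrinks. As an illustration, keep the reported shift, assume equal SDs and use t = d/√(1/n + 1/m), where m is the reference size. If all non-repeat pairs over two hours apart qualify (615/1,863 = 33%), m is about 0.33×460 = 152 for cell 22, and its minimum d of 0.27 gives p = 0.034. If only pairs at least a day apart qualify (6% to 18% of non-repeats), m is about 29 to 82 and p is 0.21 to 0.07. For cell 44 (d = 0.49), m of about 159 gives p = 0.019, and m of about 30 to 86 gives p = 0.07 to 0.028. A weaker p-value after the change could therefore reflect the smaller reference alone, so estimates and intervals should be reported alongside it.
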